information). The clinicians will also be asked to make a Recruitment Brochure available to potentially eligible patients (those with lower extremity or diabetic foot ulcers over 8 weeks duration). In addition, study flyers will be sent to select VA wound and podiatry offices in the NF/SG VHS. Providers will be asked to contact study team if any patient is willing to hear about the study. If the patient is willing to hear about the study, they may contact a study team member from the contact number on the recruitment brochure or the provider can let the patient know when the research team member is scheduled to be in the provider clinic office and the patient may talk directly to the research study team member for more information. If patients call a research team member, they will have their questions answered but will not be screened over the phone. They will be scheduled to come into the provider office to discuss the study with a research team member and review informed consent. Members of the research study team will review the informed consent with the patient and enroll the subject if they agree to participate. Wound clinicians will not be asked to consent subjects, or to provide a list of patients or appointment times to research team. However, the subject's wound providers (clinicians) will be the ones to perform the sample collection and apply the LDT or bedside sharp debridement. The sample also includes one available caregiver of the patient (non-professional) to answer the caregiver surveys if willing, and the wound care providers, who will be asked to answer the clinician survey regarding perceptions of debridement methods.

Sample Size Power Analysis: Power analysis is based on the patient sample and the primary study aim of comparing debridement methods on clinical effectiveness. The POWER procedure in SAS version 9.2 (Cary, N.C.) was used to conduct the power analysis. Assuming a Type I error rate of .05 and two-sided testing, a sample of 64 is needed in each group to detect a medium effect size of .50 with at least 80% power. This magnitude of effect is considered clinically significant.

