Patient characteristics to be recorded: Age (in years), gender (Male/Female), presence of diabetes diagnosis (any "no" would be excluded from study), smoking behavior (Yes/No), presence or absence of pedal pulses (Yes/No) and Ankle Brachial Index (ABI), relevant laboratory values, culture reports and other pertinent medical history (co-morbid conditions). Additionally, telephone numbers will be obtained, with the participants consent, in order to call and remind the participant the day before there next upcoming visit.

Inclusion criteria: (1) Veterans over 21 years of age; (2) with chronic lower extremity or diabetic foot ulcers (wound duration over 8 weeks); (3) who at the clinician's judgment requires wound debridement (25% or more of wound bed covered with non-viable tissue); (4) wound size 1.5 cm (roughly the size of a quarter) or larger in diameter.

Exclusion criteria: (1) Cognitive impairment that would interfere with patient signing own Informed Consent; (2) Veterans on active anticoagulant therapy with most recent (within last week) PT/INR (international normalized ratio of prothrombin time) > 3.0, or other significant bleeding risk; (3) Active immune suppression just prior to or during study (on systemic corticosteroids* within 7 days prior, or chemotherapy for cancer or RA treatment within 4 weeks prior to study, or with diagnosis of HIV/AIDS) - *Nasal steroid sprays will not be excluded; (4) Active systemic antibiotics is an exclusion; (5) Absent dorsalis pedis pulses and Ankle Brachial Index (ABI) < 0.5 is an exclusion (indicates critical limb ischemia). Other possible reasons participants could be removed from this study include: transfers to other non-VA facilities, participant is unable to tolerate tissue sampling even with local anesthesia, at the discretion of the provider for clinical reasons, and/or inability to comply with scheduled research visits. Furthermore, if the participant has significant wound healing so that sampling is not possible after the initial sampling, they will be removed from the study.

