X post-measure (**sample 2**); Pain survey; photos
Apply larvae bag 2
- Day 8 - **X** final measures (**sample 3**); surveys; photos

SD group

- Day 0 - **X** pre-measures (**sample 1**); surveys; photos
Sharp Debridement 1
- Day 4 - **X** post measures (**sample 2**); pain survey; Wound photos
- Day 7 - Sharp debridement 2 & photos
- Day 8 - **X** final measures (**sample 3**); surveys; photos

Data Collection & Data Management

Measurement of bacterial colonization. A microbiological assessment of the wound samples will be performed. Samples will be measured for both planktonic (single) bacteria and biofilm bacteria by standard clinical microbiology techniques with serial dilution and plating on complete agar medium

plates. Colony forming units (CFUs) will be measured after approximately 24 hours of culture under standard laboratory conditions. Levels of planktonic bacteria and biofilm bacteria will be compared within each sample and chronologically within each patient. Photos will be reviewed by blinded wound clinicians and rated on amount of necrotic tissue present visually in wound bed at each sampling time (reported on scale 0 – 10 based on 0%, 1 = 10% or less, etc.). Data collected from human subject's electronic health record will include characteristics such as wound etiology, wound location/duration, wound treatments, wound photos, wound progress notes, age, gender, comorbid conditions, pertinent laboratory values and medical history. This data will be conducted only by trained research team members designated in the IRB approved study protocol over the duration of the study.

Only de-identified pertinent information per subject sample such as age of subject, visit number (Day 0, 4, 8), location of wound, duration of wound, co-morbid conditions, medications and current wound treatments will be shared with the investigational laboratories or their personnel. Only the PI, site PI, Co-Investigators, and study coordinator(s) will have access to the subject PHI and study folders. UF lab has agreed to destroy any remaining samples at the conclusion of the current study.

Measurement of MMPs. Using techniques such as ELISA or fluorescence resonance energy transfer (FRET) assay methodology, the levels of active MMPs (or measures of MMP activity) will be calculated and expressed as pg/ml of wound fluid and pg/mg protein.

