Measurement of IL6. Using techniques such as ELISA and fluorescence resonance energy transfer (FRET) assay methodology, the levels of active IL6 will be calculated and reported.

Methods for Data Collection & Data Management

Variable	Significance	Sampling time	Source	Specific Aim
Age	Demographic	Baseline	EHR	n/a
ABI	Exclusion criterion	Baseline - enrollment	ABI done after ICF	n/a
% nonviable wound tissue	Appearance of wound bed	Baseline Day 0 and Day 8	Provider assessment	Aim 1
Quantitative Cultures (planktonic and biofilm)	Microbial identification	Day 0 (pre-test), + Day 4 and Day 8	Wound samples	Aim 1
Wound Size in cm ² (volume: L x W x D)	Descriptive	Baseline Day 0 and Day 8	Wound measurements	Aim 2
Interleukin 6	Marker of inflammation	Day 0 (pre-test), + Day 4 and Day 8	Wound sample (fluid and/or tissue)	Aim 2
Matrix metalloproteinases (MMP-2 and 9 equivalent)	Elevated MMPs associated with non-healing wounds	Day 0 (pre-test), + Day 4 and Day 8	Wound sample (fluid and/or tissue)	Aim 2
Perceptions of therapy	Perceptions of debridement	Day 0 (pre-test) + Day 8	Patient, Caregiver & Clinician Surveys	Aim 3

Survey Methods

Subjects will be asked to complete a paper survey at Day 0, Day 4 and Day 8 of the study, querying the patient's perceptions of: wound pain, satisfaction with most recent/current wound care method, ease of

care, effectiveness of most recent wound treatment, aesthetics of current wound treatment and toward sharp debridement and maggots for wound care.

Caregivers and wound clinical providers will be asked to complete a paper survey at Day 0 and Day 8 of the study (if wound clinician is caring for more than one study subject, they will be asked to complete a survey at day 0 of first subject, day 8 of first subject and 3 months later or at completion of the study for each type of debridement), querying them about their perceptions of what the patient's experience was regarding the most recent wound debridement methods as well as satisfaction with most recent/current wound care method, ease of care, effectiveness of most recent wound treatment, aesthetics of most current wound treatment and toward sharp debridement and maggots for wound care.

Data Analysis

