Data will be summarized with descriptive statistics. Data will be checked for implausible values, missingness, and distributional form. Data transformations will be made as necessary to achieve normality. To address Specific Aim 1 (comparing the clinical effectiveness of a self-contained larval debridement therapy with a bedside sharp debridement therapy), the numeric outcome measures of changes (post minus pre) in percent of non-viable tissue and bacterial biofilm will be analyzed using independent samples t-tests. To address Specific Aim 2 (comparing wound characteristics of larval debridement and bedside sharp debridement therapies) over time, longitudinal generalized mixed models (GLMMs) will be used with the dependent repeated measures being wound characteristics (e.g., inflammatory markers, wound size) and the independent variable of group assignment (larval versus sharp debridement). To address Specific Aim 3 (investigating patient, caregiver, and clinician perceptions of larval therapy dressings and bedside sharp debridement using self-reported assessments, independent samples t-tests will be used to analyze data measured at the interval level, Wilcoxon rank sum tests will be used to analyze data measured at the ordinal level, and chi-square tests (or Fisher exact tests in the case of data sparseness) will be used to analyze categorical data. All hypotheses testing will be two-sided using a level of significance of .05. Data will be analyzed as "intent to treat." SAS version 9.2 (Cary, N.C.) will be used for all analysis.

Data and Safety Monitoring Plan

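### The Aim 1 change-score t-tests are valid, but adjusting for the Day 0 value (ANCOVA) would use data already collected at almost no cost; the gain depends on SDs and a correlation the documents do not give

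*Combined protocol and SAP*

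**What the plan says.** The Data Analysis section states for Specific Aim 1 that "changes (post minus pre) in percent of non-viable tissue and bacterial biofilm will be analyzed using independent samples t-tests". It names no covariate for this aim. The mixed models in that section belong to Specific Aim 2, and the abstract's general mention of bivariate and multivariate analysis commits Aim 1 to no adjustment. The section also provides for checking distributions and transforming data where normality requires it.

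The table under Methods for Data Collection & Data Management lists both Aim 1 outcomes with a Day 0 value. The row for "nonviable wound tissue" has Day 0 and Day 8. The row for "Quantitative Cultures (planktonic and biofilm") has Day 0, Day 4 and Day 8.

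The sampling timeframe for the sharp debridement group labels Day 4 as "post measures (sample 2); pain survey; Wound photos" and Day 8 as "final measures (sample 3); surveys; photos". The larval group's schedule uses the same two labels.

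The Sample Size Power Analysis, given once for each site, plans 64 per arm to detect an effect size of 0.50 with at least 80% power at a two-sided 0.05 level. It gives no SD and no correlation between Day 0 and later values, and does not say which SD scales the 0.50.

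**The concern.** A change score is the Day 8 value minus exactly one times the Day 0 value. If the regression of Day 8 on Day 0 within arms has a slope other than 1, the change score carries Day 0 variation that adjustment would remove, and the test loses precision. The trial is powered on Aim 1 with no slack, so precision obtainable from measurements already planned is worth having. If the slope happens to be 1, the two analyses are practically the same.

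For biofilm, the plan must also say which sample is the post value, because samples are taken on both Day 4 and Day 8 and the schedule attaches the word to Day 4. For tissue, the data-collection table lists only Day 0 and Day 8.

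**Working it through.** **Inputs from the documents.** 64 per arm, effect size 0.50, two-sided 0.05 (Sample Size Power Analysis); t-test on change (Data Analysis).

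**Assumed inputs, because none are given.** Correlation r between Day 0 and Day 8 from 0.3 to 0.9; ratio k = Day 8 SD / Day 0 SD from 0.75 to 1.5; the 0.50 read in units of the change-score SD, the natural reading since change is what the t-test analyses.

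**1. The plan's own figure.** Noncentrality = 0.5 × √(64/2) = 0.5 × √32 = 2.828, with 126 degrees of freedom. Power is 80.15%. At 63 per arm it is 79.5%, so 64 is the smallest size that reaches 80%. The planned figure is reproduced.

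**2. Relative variance.** In units of the Day 0 variance, the change score has variance 1 + k² − 2rk, and the ANCOVA residual has variance k²(1 − r²). Their ratio is

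V = k²(1 − r²) / (1 + k² − 2rk).

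At k = 1 this is (1 + r)/2. V never exceeds 1, and equals 1 only when rk = 1, that is, when the true slope is 1.

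**3. ANCOVA power.** Noncentrality = 2.828/√V, with 125 degrees of freedom. Each cell gives V, then power.

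| k | r = 0.3 | r = 0.5 | r = 0.7 | r = 0.9 |
|---|---|---|---|---|
| 0.75 | 0.460, 98.5% | 0.519, 97.4% | 0.560, 96.3% | 0.503, 97.7% |
| 1 | 0.65, 93.6% | 0.75, 90.0% | 0.85, 86.1% | 0.95, 82.1% |
| 1.25 | 0.784, 88.7% | 0.893, 84.4% | 0.981, 80.9% | 0.950, 82.1% |
| 1.5 | 0.871, 85.2% | 0.964, 81.5% | 0.998, 80.2% | 0.777, 88.9% |

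The largest gain is 98.5 − 80.1 = 18.4 points, at k = 0.75. At k = 1 the largest is 93.6 − 80.1 = 13.5 points. In the rows with k above 1 the gain is between 0.1 and 8.8 points.

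**4. Worst case.** At rk = 1 (for example k = 1.25, r = 0.8), V = 1 and power is 80.1%. Chance Day 0 imbalance multiplies the variance by about 1 + 1/124, which gives 79.8%. The loss is 80.1 − 79.8 = 0.3 points.

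**5. Check by simulation** (20,000 trials per setting, k = 1). Type I error was 4.9 to 5.1% for the t-test and 4.8 to 5.1% for ANCOVA. ANCOVA power was 93.4, 89.8, 85.6 and 82.1% at the four correlations, in line with the formula.

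**6. Biofilm counts at a detection limit.** Assumed throughout: log10 means 5 (Day 0) and 4 (Day 8), Day 0 SD 1.25, and 10% or 30% of control Day 8 counts at the limit. With equal SDs both tests lose power and ANCOVA leads: at 10% and r = 0.3, 70.4% for the t-test against 91.6%; at 30% and r = 0.9, 40.2% against 60.4%. With a larger Day 8 SD the lead can vanish: at k = 1.25, r = 0.9 and 10%, 75.0% for the t-test against 74.7%; at k = 1.5, r = 0.7 and 10%, 76.0% against 76.1%.

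**The case against.** The strongest reply is that nothing is broken. The test is valid, the sample size is right for it, and the gain may be nil and cannot be known in advance. All of that stands, and it is why this is an improvement and not an error.

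A reader might infer more in four places, and the documents do not support it.

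- **That the entry rule shows the slope is not 1.** Patients need "25% or more of wound bed covered with non-viable tissue" at entry, which cuts off low Day 0 values only. But selecting on the Day 0 value does not move a linear slope: it lowers r and raises k while the product stays put. In a check with assumed normal values truncated at 25% and a true slope of 1, r went from 0.88 to 0.82 and k from 1.14 to 1.22, with rk at 1.00 both times; with a true slope of 0.6, rk stayed at 0.60. The case for ANCOVA is that the slope is unknown, not that it is known to differ from 1.
- **That ANCOVA always wins clearly for biofilm.** Step 6 shows that a clear lead at equal SDs does not carry over to a larger Day 8 SD.
- **That the t-test has 80.1% power without condition.** If the 0.50 were in Day 8 SD units with equal SDs, the t-test would have 66.0, 80.1 and 95.2% at r = 0.3, 0.5 and 0.7, against 83.7, 90.0 and 97.6% for ANCOVA. The figure also needs 128 analysed: 140 less 10% is 126, or 63 per arm and 79.5%.
- **That transformation is ignored.** The Data Analysis section already provides for it; only the scale and the handling of zero counts are left open.

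The conflict between the blinded photo rating and the provider assessment of tissue is a separate point. Changing the source would change the assessor and the scale of the outcome, which goes beyond a change of analysis.

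**Conclusion.** The concern holds as a free improvement. The Aim 1 t-tests are valid under randomisation and meet the planned power on the change-score reading with 128 analysed. ANCOVA on the Day 0 value does at least as well apart from a loss of about 0.3 points at worst. Its gain is nil when r times the SD ratio is 1, 2 to 13 points at equal SDs, and about 18 points at most, at an SD ratio of 0.75. These gains rest on assumed correlations and SD ratios and on roughly normal outcomes. ANCOVA does not remove the floor of a bounded tissue score or of undetectable counts. Validity here concerns the form of the test only, not how patients removed from the study are handled.

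**What to change.** In Data Analysis, replace the Aim 1 t-tests with ANCOVA: the Day 8 value as outcome, arm as factor, and the Day 0 value of the same measure, on the same scale, as covariate. For biofilm, use log10 counts at both days and fix in advance the value that stands in for a zero count; this makes the transformation already foreseen specific. State that Day 8 is the post day for biofilm and align the labels in the sampling timeframe.

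Keep 64 per arm, since the gain cannot be counted on, and state which SD the 0.50 refers to.

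The cost is wording and one degree of freedom: no added patients, visits or samples. The source of the tissue rating should be settled separately.

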To compare the clinical effectiveness of a self-contained bagged larval debridement therapy (intervention) (BioBag) with bedside sharp debridement (control). The following comparisons will be made: 1) The visual reduction of non-viable tissue in the wound bed of chronic full-thickness lower extremity or diabetic foot ulcers, and 2) The reduction in colony forming units (CFU) of bacterial biofilm in samples taken from the wound bed.

Specific Aim 2

To compare wound characteristics (e.g., inflammatory markers, wound size) in the intervention group (BioBag therapy) and control group (Sharp debridement) over time.

Specific Aim 3

To investigate patient, caregiver and clinician perceptions of larval therapy dressings and bedside sharp debridement using measures of self-reported aesthetics, ease of use, and wound pain.

6. Research Plan:

Research design and methods

Design: A repeated measures, randomized control trial experimental design will be used for this study. Subjects will serve as their own control, in addition to a control group. Initial wound samples will be followed by two subsequent repeated wound samplings approximately four days apart. Informed consent will be obtained prior to all procedures, photo consents will also be obtained for wound photos.

Veteran Site: North Florida South Georgia Veterans Health System

Setting, Sample: A target goal final sample size of one hundred twenty eight adults from the North Florida South Georgia VHS will be recruited (total recruited number anticipated to be ~140 allowing for 10% attrition). Including target of 128 Caregivers and 6 Providers, and accounting for 12 caregivers lost to follow up or 10 subjects who fail screening, the total study recruitment population is 296. Wound providers and clinicians who care for lower extremity or diabetic foot ulcers will be provided with a "Provider Study Flyer" which gives a brief description of the study with inclusion/exclusion criteria listed (to remind the Provider to approach potentially eligible patients with Research Team Contact

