Larval Debridement Therapy (intervention) group: Briefly, wounds may be rinsed with saline and blotted with sterile gauze prior to collecting baseline wound samples at Day 0. Wound measurements and wound photos will be taken at baseline and Day 8. Wound samples will be collected on Day 0, Day 4, and Day 8. One BioBag (larval debridement therapy) will be applied to wound on Day 0 after baseline wound samples are obtained, and this will be removed on Day 4, at which time 2nd wound sample is obtained. Immediately after 2nd wound sample obtained, the 2nd BioBag will be applied. The dead larvae from the Biobags after removal from the subjects in this study will be placed in a sterile container and labeled with study subject number and "1st" or "2nd application." These specimens will be frozen in our VA research laboratory for a future secondary analysis. This will be the subject of a new grant proposal being submitted by the current investigators in 2015 with the aim of examining the digestive track and body of the larvae for the presence of bacteria and correlating this with the bacteria identified in the bacterial analysis of the subject wounds. Size of the Biobag is determined by the size of the wound (typically 5 to 8 larvae per cm² or 50 to 400 larvae per single Biobag). Only cover dressing (saline moistened gauze + dry gauze/secondary cover) will be changed over BioBag on days 1,2,3,5,6, and 7. Last wound sampling (3rd) will be done on Day 8, after 2nd BioBag is removed. Clinicians as well as Veteran participants and non-Veteran participants (at NFRMC) and their caregivers will be given copies of LDT instructions for use (Appendix A/Appendix B). Wound samples will be obtained at each

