sampling date by sterile swab(s) and 3-4mm curette scraping of wound bed using a sterile curette sweeping z track method across wound bed. Sterile filter paper or micropipette/capillary tube may also be used to collect wound fluid. Wound samples will be collected at wound provider's office/clinic and placed in appropriate receptacle (sterile transport tubes with caps or vials with caps) for transport. The sample receptacles will be labeled with assigned subject number, number of visit (1, 2, 3, etc.), date of sample collection, duration and location of wound. Labeled samples will be placed in sealed biohazard bag, then in a biohazard marked cooler with a cold pack, and this container will be placed in a larger transport container for transport to the VA laboratory. Clinicians and clinic staff will be asked to complete sample collection training and biohazard shipping (if shipping is deemed necessary) training before collecting or shipping any wound samples to standardize the procedures and be in compliance with research, safety and shipping regulations. Clinicians will be asked to view a LDT training video before performing application of Larvae in order to further standardize the application.

[figure not shown]
Sharp Debridement Therapy (control) group: Briefly, wounds may be rinsed with saline and blotted with sterile gauze prior to collecting baseline wound samples at Day 0. Wound measurements and wound photos will be taken on Day 0, Day 4, Day 7 (before and after sharp debridement) and on Day 8. Wound samples will be obtained on Day 0, Day 4, and Day 8. Sharp debridement will be performed by patient's wound clinician using standard technique on day 0 after baseline wound measures are obtained and again on day 7. Wound samples will be obtained by sterile swab(s) and 3-4mm curette scraping of wound bed using a sterile curette sweeping z track method across wound bed. Sterile filter paper or micropipette/capillary tube may also be used to collect wound fluid. Wound samples will be placed in appropriate receptacle for transport as described above. Wound gel dressing (with gauze as secondary cover) will be applied to wound after debridement and changed daily as a control dressing. The following depicts the anticipated sampling timeframe for each participant.

LDT group (X denotes sampling procedure)

- Day 0 - **X** pre-measures (**sample 1**); surveys; photos
Apply larvae bag 1
- Day 4 - Remove larvae bag 1

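### The Aim 2 mixed model names group as its only predictor and leaves visit, the Day 0 value and the tested contrast unstated; fitted as written, it dilutes the treatment effect.

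*Combined protocol and SAP*

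**What the plan says.** Specific Aim 2 reads: "To compare wound characteristics (e.g., inflammatory markers, wound size) in the intervention group (BioBag therapy) and control group (Sharp debridement) over time". The only text on its analysis is in the Data Analysis section, which calls for a longitudinal generalized mixed model with "dependent repeated measures being wound characteristics (e.g., inflammatory markers, wound size) and the independent variable of group assignment (larval versus sharp debridement". No other predictor is listed.

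The same paragraph does say how baseline enters for Aim 1, where the outcomes are "the numeric outcome measures of changes (post minus pre) in percent of non-viable tissue and bacterial biofilm". Nothing equivalent is said for Aim 2.

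The table under Methods for Data Collection & Data Management gives the Aim 2 schedules. IL-6 and MMPs are taken at "Day 0 (pre-test), + Day 4 and Day 8" and wound size at "Baseline Day 0 and Day 8". Day 0 precedes treatment in both arms.

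The Design paragraph describes a repeated-measures trial in which patients also act as their own controls. It does not translate this into model terms.

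**The concern.** Several models fit the Aim 2 sentence: a group main effect over all visits, a difference in change from Day 0, a Day 8 difference, or an average over Days 4 and 8, with or without adjustment for Day 0. They estimate different quantities, and the plan does not choose among them. The choice could therefore be made after the data are seen.

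The model as written is also the least favourable for wound size. Randomization leaves no expected difference at Day 0, so a group coefficient that pools Day 0 with treated visits is pulled towards zero. At stake are the comparisons of wound size, IL-6 and MMPs. The primary aim and the sample size are not affected.

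**Working it through.** **Inputs from the document.** 64 per arm, two-sided 5%, effect 0.50 SD (Sample Size Power Analysis); visits as in the data collection table. The 0.50 was set for the primary aim and is borrowed here.

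**Assumptions, not in the document.** SD 1 at each visit; the same correlation r between any two visits, taken as 0.3, 0.5 and 0.7; complete data; no expected Day 0 difference. A sustained effect means the same difference d at every post-treatment visit.

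**1. The plan's own figure.** The plan states that "a sample of 64 is needed in each group to detect a medium effect size of .50 with at least 80% power". SE = √(2/64) = 0.177; 0.5/0.177 = 2.83; noncentral t with 126 df gives 80.1% power (79.5% with 63 per arm). The figure reproduces.

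**2. What the group coefficient estimates.** With balanced visits it is the average of the visit differences.
- Days 0, 4, 8, sustained: (0 + d + d)/3 = 0.67d.
- Days 0, 8: (0 + d)/2 = 0.50d.
- Days 0, 4, 8, effect only at Day 8: (0 + 0 + d)/3 = 0.33d.

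**3. Does a visit main effect help?** No. In balanced data it leaves the group estimate unchanged. Random-intercept fits to simulated data with a common time trend of 0.5 SD gave group coefficients that differed by less than 1e-14 with and without it.

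**4. Power for a sustained d = 0.5.** SE = √((2/64) × V); noncentral t with 126 df, or 125 df when adjusted.

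| Test | Effect estimated | V | r = 0.3 | r = 0.5 | r = 0.7 |
|---|---|---|---|---|---|
| Group only, Days 0, 4, 8 | 0.333 | (1+2r)/3 | 73% | 63% | 55% |
| Group only, Days 0, 8 | 0.250 | (1+r)/2 | 41% | 37% | 33% |
| Day 8 minus Day 0, unadjusted | 0.500 | 2(1−r) | 66% | 80% | 95% |
| Day 8, adjusted for Day 0 | 0.500 | 1−r² | 84% | 90% | 98% |
| Mean of Days 4 and 8, adjusted for Day 0 | 0.500 | (1+r)/2 − r² | 96% | 98% | >99% |

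Example for wound size at r = 0.5: both the group-only and the adjusted Day 8 tests have V = 0.75 and SE = 0.153. The first has 0.25/0.153 = 1.63 (37%), the second 0.50/0.153 = 3.27 (90%). The precision is the same, but the effect is halved.

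Simulation (20,000 runs per setting) agrees within one percentage point. With no effect and equal visits the group-only tests reject 4.6-5.3% of the time.

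**5. Source of the gain.** With three visits, the unadjusted change contrast matches the group-only test when (4/9)/((1+2r)/3) = 1/(2(1−r)), that is 8(1−r) = 3(1+2r), so r = 5/14 = 0.36. Below that it is the weaker test (66% against 73% at r = 0.3). A group-by-visit term alone therefore does not guarantee more power; over the range shown, the consistent gain comes from adjusting for Day 0. At very low correlation even the adjusted Day 8 test loses to the three-visit group-only test: 4(1−r²) = 3(1+2r) gives r = 0.15.

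**6. Sensitivity.**
- Two visits, d = 0.3: 15-18% group-only against 42-66% for adjusted Day 8.
- Two visits, d = 0.8: 68-80% against over 99%.
- Three visits, effect (d = 0.5) only at Day 8: 25/21/18% group-only and 47/51/65% for the adjusted Day 4/8 mean. Adjusted Day 8 keeps 84/90/98%. The best contrast thus depends on the effect pattern, which is why it must be named in advance.

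**7. Separate consistency check on wound size.** Under Study procedures, the larval arm has "Wound measurements and wound photos will be taken at baseline and Day 8" and the control arm "Wound measurements and wound photos will be taken on Day 0, Day 4, Day 7 (before and after sharp debridement) and on Day 8"; the table gives Days 0 and 8 for both. If every control-arm measurement were pooled with no time term and both arms changed linearly by T by Day 8, the arm averages would be (0 + 1)T/2 = 0.50T and (0 + 0.5 + 0.875 + 0.875 + 1)T/5 = 0.65T, a spurious gap of 0.15T. Simulated false rejection is below 6% for T = 0.25 SD, 8-9% for 0.5 SD and 16-21% for 1.0 SD.

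**The case against.** The strongest reply is that nobody would fit the group-only model. The Aim 2 analysis is described as longitudinal and over time, the design has patients act as their own controls, and Day 0 is labelled a pre-test. On that view the power loss belongs to an unlikely reading, and what remains is a wording gap in a non-primary aim.

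Much of this stands. A reader might infer that time will be left out of the analysis. The document does not show that; it shows only that group is the one predictor named. A reader might also infer that dilution is unavoidable for wound size because Day 8 alone is not a repeated measure. That holds only on the group-only reading: two visits with a group-by-visit term recover the full difference in change. The table, moreover, labels wound size as descriptive, although it also assigns it to Aim 2 and the analysis text names it in the model.

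The reply does not remove the point. Recognising that time matters does not choose among the models, and the most natural minimal repair, a visit main effect, leaves the diluted group estimate as it was. The best use of the Day 0 value appears nowhere in the Aim 2 text.

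**Conclusion.** The concern holds as underspecification with a quantifiable cost on the literal reading. As written, the group coefficient recovers 0.67 (three visits) or 0.50 (two visits) of a sustained effect. Those fractions need only balanced visits and no expected Day 0 difference. The power figures are illustrations: they rest on a borrowed effect size, assumed correlations and compound symmetry.

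Three stronger conclusions are not supported. The test is not invalid when both arms have the same visits. The trial cannot be called underpowered for Aim 2, because no effect size or power target is given for it. The inflated false rejection from unequal measurement days is conditional on pooling all control-arm days without a time term and on a material change in both arms; it is not a consequence of the plan as such.

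This should be settled before analysis. It does not touch the primary aim or the 64 per arm.

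**What to change.** State the Aim 2 model in full:

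- **IL-6 and MMPs:** model the Day 4 and Day 8 values on group, visit, group-by-visit and the Day 0 value, or use an equivalent constrained-baseline model that keeps Day 0 in the response. Name the tested contrast in advance: the Day 8 difference or the Day 4/8 average.
- **Wound size:** model the Day 8 value on group and the Day 0 value, using only the days common to both arms.

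Keeping Day 0 in the response with a group-by-visit term and an unadjusted change contrast would also answer the question over time, but with less power than baseline adjustment.

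As separate minor points, reconcile the wound-measurement days between the two Study procedures paragraphs and the data collection table. Reconcile also the wound-size row of that table, which gives an area unit (cm²) but defines the quantity as a length-width-depth volume.

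The cost is analysis wording and the reconciliation of these entries. Every variable needed is already collected.
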